4.0 Study design

The study followed a randomized, active placebo-controlled, double-blind design, with subjects, psychotherapists and independent raters blinded to participant condition. Twelve subjects with treatment-resistant PTSD were randomly assigned after baseline assessment to receive either full dose of 125 mg MDMA followed by a supplemental dose of 62.5 mg MDMA administered 2.5 h

later, or to an active placebo dose of 25 mg MDMA followed by 12.5mg MDMA 2.5h later. Participants underwent three sessions of MDMA-assisted psychotherapy scheduled to occur three to five weeks apart, 1 non-drug-psychotherapy session 24 h after each MDMA-session and 2-4 weekly integrative psychotherapy sessions after each MDMA session. PTSD symptoms were assessed by an independent rater once prior to MDMA-assisted psychotherapy, three weeks after the second MDMA-assisted session, three weeks after the third experimental session. After unblinding, active placebo participants had the opportunity to take part in an open-label continuation of the study, referred to here as "Stage 2." Data gathered three weeks after the third experimental session was treated as the baseline for Stage 2, and outcome measures were administered three weeks after the second and third experimental session. Originally outcome measures would also be given two, six and twelve months after the third experimental session, but the six-month evaluations were discontinued after January 2009 in line with the Amendment 5 of the protocol. Participants receiving the full dose in either Stage 1 or Stage 2 who did not show significant improvement in PTSD symptoms were offered the opportunity to take part in an open-label continuation of the study, "Stage 3", consisting of two additional MDMA sessions. During these sessions, they could receive 125 mg followed 2.5 hours later by 62.5 mg MDMA or a 20% larger dose of 150 mg MDMA, followed by a supplemental dose of 75 mg administered 2.5 hours later, unless contraindicated by safety parameters. Outcome measurements gathered at 2 months after the third experimental session will serve as baseline measures for Stage 3. Stage 3 was also cancelled in line with Amendment 5. Of the 12 participants who completed the study, only three participants underwent Stage 3.

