6.0 Analyses

6.1 Study population

See protocol. All participants were diagnosed with chronic PTSD, met DSM IV criteria, and had Global CAPS scores of 50 or greater upon enrollment. They had either undergone psychotherapy, pharmacotherapy or both without a significant reduction in PTSD symptoms.

All clinical data will be presented in tabular listings. All analyses will be carried out with SPSS of Version 12.0 or higher.

Definitions of subject populations for analysis:

All Enrolled: All participants who signed an informed consent form and completed baseline measures.

Intention to treat: All participants who were randomized to a condition and underwent at least one experimental session. All available data will be used.

Per Protocol: All participants who completed Stage 1 and underwent assessment of PTSD symptoms two months after the second experimental session. Analyses may be conducted with and without a participant who corresponds to a major protocol deviation.

Partial crossover: All participants who completed Stage 2 as well as Stage 1.

Extended Assessment 1: All participants who underwent assessment two, six and twelve months after their third Stage 1 or Stage 2 experimental session.

Extended Assessment 2: All participants who underwent Stage 3

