6.2 Protocol Deviations

All protocol deviations will be included as a categorized listing. Subjects with minor deviations will be included in all analyses. Analyses will be performed with and without deviations to examine the effects of including them in an analysis. Secondary analyses may be conducted to examine interactions with certain characteristics within the subject population. If it is appropriate as indicated via analyses, subjects with major deviations will be excluded from the per protocol analysis and included in the intention to treat analysis. Safety analysis will include all enrolled subjects with all available data.

Possible deviation categories include:

- Entered study but did not meet entry criteria
- Developed withdrawal criteria during the study but were not withdrawn
- Received wrong treatment or incorrect dose
- Received excluded concomitant treatment
- Protocol procedure not performed per protocol
- Protocol procedure performed out of range
- Informed consent performed not per protocol

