6.4.1 Main analyses

Goal: To determine if there is a main effect of condition on PTSD symptoms and criteria for meeting PTSD, three weeks after the second experimental session and three weeks after the third experimental session 1.

Population: Intention to Treat and Per protocol

Data included in analyses: CAPS (Global Score, subscales, and Diagnostic criteria met)

Format of analyses: Repeated-measures ANOVA. If multiple scores from a single scale are assessed, Bonferroni corrections were applied.

Time: Baseline, 3 weeks after Exp. Session 2, 3 weeks after Exp. Session 3

Between-groups factors: Condition (125 mg MDMA, 25 mg MDMA)

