6.4.2 Additional analyses

Analysis #1

Goal: To determine if there is a main effect of condition on self-reported PTSD symptoms for meeting PTSD criteria, three weeks after the second experimental session and three weeks after the third experimental session 1.

Population: Intention to treat and Per protocol

Data included in Analyses: PDS Severity Score

Format of analyses: Repeated measures ANOVA

Between-groups Factor: Condition (125 mg MDMA, 25 mg MDMA)

Analysis #2

Goal: To determine if there is a main effect of condition and participation in partial crossover upon PTSD symptoms, meeting PTSD diagnostic criteria, and reduced psychological symptoms three weeks after the third experimental session, and three weeks after the third Stage 2 session.

Population: Intention to Treat, Per Protocol and Partial Crossover

Data included in analyses: CAPS (Global Score and subscales specified above, Diagnostic criteria met, Associated Features), PDS (Severity Score, Rating, Impairment)

Format of Analyses: Repeated measures ANOVA. If multiple scale scores from a single measure are analyzed, Bonferroni corrections will be applied.

Time: Baseline, 3 Weeks after Stage 1 Experimental Session 3, 3 weeks after Stage 2 experimental session 3

Between-groups factors: Condition (125 mg MDMA, 25 mg MDMA)

Analysis #3

Goal: To test for an effect of Stage on PTSD symptoms and meeting criteria for PTSD.

Population: Intention to Treat, Per Protocol and Partial crossover

Data included in analyses: CAPS (Global Score and subscales specified, Diagnostic criteria met, Associated Features), PDS (Severity Score, Rating, Impairment)

Format of Analyses: Repeated measures ANOVA or independent t-tests. If multiple scale scores from a single measure are analyzed, Bonferroni corrections will be applied.

Time: Baseline, 2 months after Stage 1 3rd Experimental Session, 2 months after 3rd Stage 2 Experimental Session

Between-groups factors: Condition (125 m MDMA, 25 mg MDMA)

Analysis #4

Goal: To determine whether there is a continued effect of MDMA-assisted psychotherapy 2, 6 or 12 months after the third experimental session through formal or informal analyses

Population: Extended Assessment 1

Data included in Analysis: CAPS (Global Score, Diagnostic criteria Score, Associated Features), PDS (Severity Score, Rating, Impairment)

Format of Analysis: Informal comparison of descriptive data for the three participants who underwent 2, 6 and 12 month assessment.

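### The SAP's Per Protocol set depends on a visit that no supplied schedule contains, and exclusion of major deviators can depend on results

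*SAP*

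**What the plan says.** **The set.** SAP 6.1 defines the set as follows: "Per Protocol: All participants who completed Stage 1 and underwent assessment of PTSD symptoms two months after the second experimental session". In the same list, Extended Assessment 1 counts from session 3: "All participants who underwent assessment two, six and twelve months after their third Stage 1 or Stage 2 experimental session".

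**The schedule.** Protocol 2.8.2 lists six PTSD assessments: baseline (T0), 3 weeks after session 2 (T1), 3 weeks after session 3 (T2), and 2, 6 and 12 months after session 3 (T3 to T5). SAP 4.0 has baseline, then "three weeks after the second MDMA-assisted session, three weeks after the third experimental session", and follow-up at 2, 6 and 12 months after session 3, with the six-month visit later dropped under Amendment 5. SAP 4.1 refers to an attached time-and-events table, which is not in the supplied text.

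**Use.** The main CAPS analysis (SAP 6.4.1) is run on both Intention to Treat and Per Protocol, with "Time: Baseline, 3 weeks after Exp. Session 2, 3 weeks after Exp. Session 3". Analysis #3 in SAP 6.4.2 has "Time: Baseline, 2 months after Stage 1 3rd Experimental Session, 2 months after 3rd Stage 2 Experimental Session".

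**Deviators.** SAP 6.1 says "Analyses may be conducted with and without a participant who corresponds to a major protocol deviation". SAP 6.2 says "Analyses will be performed with and without deviations to examine the effects of including them in an analysis", and then "If it is appropriate as indicated via analyses, subjects with major deviations will be excluded from the per protocol analysis". It lists seven possible deviation categories and marks none as major or minor. SAP 8.0 records that outcome data were shown at conferences in 2010 and 2011.

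**The concern.** A Per Protocol analysis checks whether the intention-to-treat result holds among participants treated and assessed as planned. It can do so only if membership is settled by a clear rule that ignores the results. This set fails on both counts. Its qualifying visit cannot be found in the schedule, and the exclusion of major deviators is left to unspecified analyses.

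The set is used widely. Of the seven efficacy analyses in SAP 6.4, six name it (the main analysis, Analyses #1 to #3, the demographic analysis and the subsidiary analysis). Only Analysis #4 does not. In the main analysis it stands beside intention-to-treat with neither called primary. With 4 low-dose participants planned (Protocol 2.8.1), a single membership decision can concern a quarter of that arm, so it should not be left open.

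**Working it through.** **Inputs.** Visits come from Protocol 2.8.2. Session spacing is 3 to 5 weeks in Protocol 2.8.4 and SAP 4.0, but 2 to 4 weeks in Protocol 2.8.1. Those statements conflict and need reconciling in their own right, so both are carried here. The plan gives no figure of its own to reproduce.

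**Step 1: where the named visit would fall.** Two months = 2 × 365.25 / 12 / 7 = 8.7 weeks after session 2. With s the spacing in weeks between sessions 2 and 3, the scheduled visits fall at these weeks after session 2:

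| Visit | Formula | s = 3 to 5 | s = 2 to 4 |
|---|---|---|---|
| T1 | 3 | 3 | 3 |
| T2 | s + 3 | 6 to 8 | 5 to 7 |
| T3 | s + 8.7 | 11.7 to 13.7 | 10.7 to 12.7 |

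T1 is 8.7 − 3 = 5.7 weeks early. T2 is 0.7 to 2.7 weeks early (or 1.7 to 3.7), and T3 is 3 to 5 weeks late (or 2 to 4). T4 and T5 are later still. The self-report PDS is also taken the day after each session, but the last of these in Stage 1 falls at most 5 weeks and 1 day after session 2. The closest match is T2 at the longest spacing, 0.7 weeks early. SAP 6.1 gives no tolerance; one admitting every on-schedule T2 at 3 to 5 week spacing would have to be 2.7 weeks. Read literally, 0 of 12 participants have the qualifying Stage 1 visit.

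**Step 2: what might have been meant.**

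- *T3, with session 2 written for session 3.* Extended Assessment 1 supports this. But T3 comes after each participant's blind is broken at T2 (Protocol 2.8.6), and of the six efficacy analyses that name Per Protocol only Analysis #3 uses it. Protocol 2.8.2 limits T4 and T5 to low-dose participants who do not enter the open-label continuation, but puts no such limit on T3. Assume the Stage 2 preparatory session takes place at T2, 3 weeks after session 3. The first open-label session is then at week 4 to 5. At the 2 to 4 week spacing of Protocol 2.8.6, 1 session (week 5, next at week 9) to 3 sessions (weeks 4, 6, 8) precede T3 at week 8.7. At 3 to 5 weeks it is 1 (week 5, next at week 10) to 2 (weeks 4 and 7). Such a T3 would be taken during open-label treatment.
- *T2.* This is where the main analysis ends and is the last assessment before unblinding.
- *A carry-over.* Protocol 2.2.3 and section 5 give this same timing for the sponsor's US study, which assessed participants two months after session 2.

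The documents do not settle which was meant.

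**Step 3: the deviation rule.** SAP 6.2 does not say which analyses decide, what they must show, or that the decision precedes sight of outcomes. With no category labelled major, both the classification and the exclusion are open. The same participant could be in or out depending on what the analyses show. Outcome data had already been presented (SAP 8.0), so the decision cannot be assumed to have been made without knowledge of results.

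**The case against.** The best defence is that the visit is a one-word slip with no shown effect. SAP 4.0 speaks of 12 participants who completed the study, and nothing shows that anyone missed T2 or T3. Either visit might therefore give the same set. On deviators, SAP 6.2 commits to analyses with and without deviations, and major deviators stay in intention-to-treat, so the discretion is partly visible. All of that stands and limits the weight of the point. It does not repair a definition that fails as written, and showing both analyses does not say who belongs to the set.

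Four stronger readings are tempting, and the documents support none of them:

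- A reader might infer that the visit exists in no schedule at all. The attached time-and-events table is missing, and the supplied protocol still contains parts that Amendment 5 ended. The claim reaches only as far as the supplied text.
- A reader might infer that the permissive sentence in 6.1 and the firm one in 6.2 contradict each other. They can be read together, with 6.2 as the operative rule.
- A reader might infer an inflated type I error. Any figure needs a rule such as reporting the smaller p-value, and the SAP states no such rule.
- A reader might count the precision lost by excluding a participant as harm from this defect. Any exclusion carries that cost, including one under a properly fixed rule.

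**Conclusion.** The concern holds in two parts. Against every supplied schedule, the literal Per Protocol set is empty. Separately, exclusion of major deviators from it is left to analyses, with major undefined, so membership can depend on results.

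The weight is minor to moderate. Intention-to-treat is untouched, and no deviation or missed visit is documented. If all 12 completers attended both T2 and T3, the choice of visit changes nobody's membership. What is weakened is the value of Per Protocol as a check on the intention-to-treat result. No numerical bias can be attached to that from the documents. The first part rests on the supplied schedules being complete for Stage 1; the second would stand even if the attached table contained the visit.

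**What to change.** Reconcile the definition in SAP 6.1 with the schedules in Protocol 2.8.2, SAP 4.0 and SAP 6.4.1. Suggested text for 6.1:

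> Per Protocol: randomised participants who completed the three Stage 1 sessions, have the end-of-Stage-1 assessment (3 weeks after session 3), and have no major deviation. Each analysis uses the CAPS or PDS time points it lists. No visit after unblinding at T2 is a condition of membership.

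This leaves Analysis #3 free to use its two-month visits without making them an entry condition. It also avoids requiring T1 for the demographic analysis, which uses only baseline and end of Stage 1. If the attached table does hold a visit two months after session 2, cite it and explain why it defines the set.

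In SAP 6.2, delete the conditional clause that opens the sentence on major deviators. State which of the seven listed categories are major. Classify each deviation without reference to condition or outcome, as far as that is still possible. Exclude major deviators from Per Protocol whatever the results, and always report the analysis that keeps them as a sensitivity analysis, with the permissive sentence in 6.1 brought into line.

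The cost is a few sentences and a short classification exercise. The main drawback is that classification can no longer be fully masked, because outcome data have been presented; the SAP should say so. A participant without the assessment 3 weeks after session 3 would leave the set, but intention-to-treat still uses that participant's available data.

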6.2 Protocol Deviations

All protocol deviations will be included as a categorized listing. Subjects with minor deviations will be included in all analyses. Analyses will be performed with and without deviations to examine the effects of including them in an analysis. Secondary analyses may be conducted to examine interactions with certain characteristics within the subject population. If it is appropriate as indicated via analyses, subjects with major deviations will be excluded from the per protocol analysis and included in the intention to treat analysis. Safety analysis will include all enrolled subjects with all available data.

Possible deviation categories include:

- Entered study but did not meet entry criteria
- Developed withdrawal criteria during the study but were not withdrawn
- Received wrong treatment or incorrect dose
- Received excluded concomitant treatment
- Protocol procedure not performed per protocol
- Protocol procedure performed out of range
- Informed consent performed not per protocol

6.3 Participant Demographics and Background

Population: All enrolled and Per protocol

Categorical Data includes: Gender, age, ethnicity/race, trauma etiology, medical history, psychiatric history, physical examination, lab values, general well being

Descriptive Data includes: Number of years with PTSD, number and duration of past therapy for PTSD, number and duration of past medications for PTSD, number of incidences of prior ecstasy use

Format of presentation: Summary tables including frequency listings in total and by condition

Content of presentation: Gender, age, ethnicity/race, trauma etiology, number of years with PTSD, number and duration of past psychotherapies for PTSD, number and duration of past medications for PTSD, number of incidences of prior ecstasy use, percent co-morbidity, as computed by summing number of current psychiatric diagnoses other than PTSD.

6.4 Efficacy Analyses

Descriptive Data includes: CAPS (Global Score, selected subscale scores, and Diagnostic criteria met), PDS (Severity Score, Rating, Impairment)

Format of presentation: Summary tables including descriptive data presented in total and by condition. Descriptive data will also be provided for any additional analyses. When applicable, summary tables divided on the basis of a given demographic variable will be provided, when demographic variables may serve as the basis for additional or subsidiary analyses, as participant age, or gender

Content of presentation: CAPS (Global Score and subscales, Diagnostic criteria met, Associated Features), PDS (Severity Score, Rating, Impairment)

6.4.1 Main analyses

Goal: To determine if there is a main effect of condition on PTSD symptoms and criteria for meeting PTSD, three weeks after the second experimental session and three weeks after the third experimental session 1.

Population: Intention to Treat and Per protocol

Data included in analyses: CAPS (Global Score, subscales, and Diagnostic criteria met)

Format of analyses: Repeated-measures ANOVA. If multiple scores from a single scale are assessed, Bonferroni corrections were applied.

Time: Baseline, 3 weeks after Exp. Session 2, 3 weeks after Exp. Session 3

Between-groups factors: Condition (125 mg MDMA, 25 mg MDMA)

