2.8.3. Data Analysis

The CAPS and PDS scores will be analyzed by nonparametric methods for analysis of variance (cf. Brunner and Langer (2002), Brunner, Domhof and Langer (2002)). The nonparametric framework is chosen for two reasons, that of the sample size being too small to assess the assumptions that underlie a parametric model, and because the primary outcome measure, CAPS score, is only measured on an ordinal scale. We will also compute descriptive statistics for Stage 1 and Stage 2 CAPS and PDS scores for all participants enrolled in Stage 2. It is unlikely that there will be enough participants in Stage 2 for formal analysis, but scores can be compared across the two stages to see whether Stage 2 scores are reduced compared with Stage 1 scores. Finally, we will compute CAPS and PDS scores for any participant undergoing “Stage 3”.

The first step of the analysis will consist of descriptively summarizing the data by graphing the time course of CAPS for each patient and by computing summary measures for CAPS. The second step will consist of testing the above-mentioned hypothesis. In order to compare the time courses of the control group and the treatment group, we will apply a so-called F1_LD_F1 (cf. Brunner and Langer (2002), Brunner et al. (2002)) with experimental intervention condition (MDMA versus active placebo) serving as a between-group factor and time of measurement serving as a within-subjects factor. We are mainly interested in testing an interaction between experimental intervention condition and time. We expect all participants will have lower CAPS scores two months after the third experimental session than at baseline, but that people given the fully active dose will have lower CAPS scores than people given active placebo. The hypothesis concerning only the treatment group will be analyzed by

comparing differences between subject's baseline CAPS and treatment scores at various time points. This can be done with Wilcoxon's Signed-Rank-Test for paired data. We expect that people will have lower CAPS scores after the third experimental session than after the second experimental session.

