1.0 Definitions

Categorical data: This refers to discrete (indivisible) variables, such as gender or ethnicity. These data will be presented as total numbers of each category as needed to describe the sample.

Descriptive data: This includes mean, median, standard deviation, minimum and maximum of numerical data used as needed to describe the sample.

Difference scores: These consist of scores computed by subtracting one value from another, as subtracting baseline from End of Stage 1 score, used to test for differences between and within groups to determine change as a function of experimental treatment over time.

Efficacy: A type of analysis used to assess therapeutic effects or benefits.

Exploratory analyses: An inferential or descriptive analysis of the data to determine trends that might lead to hypotheses for further study.

Frequency listing: A tabular listing of numbers and/or percentages of events used as needed to describe the sample or data characteristics.

Outcome measures: These are primary and secondary study measures that are used to test the study hypotheses.

Process measures: These are study measures or qualitative observations collected during the study that may increase depth of understanding and that are not necessarily related to safety or efficacy.

Protocol deviation: An event that represents significant divergence from the intended study design as described in the protocol.

Safety: An assessment of the condition of study subjects that examines potential risks, adverse events and reactions.

Safety measures: These are study measures that assess safety, such as blood pressure monitoring. These measures are used to assess safety of the study drug.

Study design: All elements of a research project that define the study question, experimental methods, study procedures including blinding and randomization, measurement techniques, flow sheet of data, and statistical analysis.

Tabular Listing: A list of each variable or item for each individual subject either in total or by condition in a table format.

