3.0 Study Objectives

As stated in the protocol, the following main questions are to be explored in the proposed study:

1. Can MDMA, in the doses to be used in this study, be safely administered in the population of treatment-resistant PTSD patients without any serious adverse events?
2. Will patients receiving the larger, fully active dose of MDMA, in combination with non-drug assisted psychotherapy, demonstrate greater symptomatic improvement than patients given an active placebo dose of MDMA in combination with non-drug psychotherapy?
3. Will patients receiving three MDMA sessions in combination with non-drug psychotherapy demonstrate an additional improvement compared to patients receiving only two sessions?
4. Can treatment effects of MDMA-assisted psychotherapy be maintained beyond end of treatment?

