3.1 Primary Objective

To evaluate changes in PTSD symptoms via CAPS scores gathered at baseline, three weeks after the second experimental session, and three weeks after the third experimental session.

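### SAP 6.4.1 makes a condition main effect that includes Baseline the main efficacy test, where protocol 2.8.3 names the condition-by-time interaction by F1_LD_F1

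*SAP*

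**What the plan says.** Protocol 2.8.3 plans rank-based analysis of CAPS and PDS. It gives two reasons: "the sample size being too small to assess the assumptions that underlie a parametric model", and CAPS being an ordinal scale. It compares the arms by F1_LD_F1, with condition between patients and time within patients, and states: "We are mainly interested in testing an interaction between experimental intervention condition and time". It sets significance at 0.05 without adjustment for multiple testing.

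SAP 6.4.1 sets a different goal: to determine whether "there is a main effect of condition on PTSD symptoms and criteria for meeting PTSD, three weeks after the second experimental session", with the same question put at the corresponding visit following session 3. The method is repeated-measures ANOVA, with Bonferroni correction when several scores from one scale are assessed. The levels are listed as "Time: Baseline, 3 weeks after Exp. Session 2, 3 weeks after Exp. Session 3". The interaction is not named.

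Elsewhere the SAP speaks of change. Its primary objective (3.1) is "To evaluate changes in PTSD symptoms via CAPS scores gathered at baseline, three weeks after the second experimental session" and the third. Question 2 in SAP 3.0 asks whether full-dose patients will "demonstrate greater symptomatic improvement than patients given an active placebo dose of MDMA in combination with non-drug psychotherapy". SAP 1.0 defines difference scores as "used to test for differences between and within groups to determine change as a function of experimental treatment over time", but 6.4.1 does not use them. SAP 4.0 says: "Twelve subjects with treatment-resistant PTSD were randomly assigned after baseline assessment".

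**The concern.** One repeated-measures model yields at least three p-values: condition, time, and their interaction. The plan has to say which one answers the efficacy question. Protocol and SAP name different ones, by different methods and with different multiplicity rules. The protocol's reasons for a rank method still apply: there are still twelve patients and the scale is still CAPS.

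The condition main effect is the difference between arms averaged over all listed Time levels. One of those levels precedes randomisation, so no treatment effect can exist there. The test therefore combines the treatment effect with whatever baseline difference chance produced, and it is not a test of greater improvement. SAP 8.0 records that outcome data were presented in 2010 and 2011, so a reader needs to know when and why the main test changed.

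**Working it through.** **Inputs from the documents.** 8 full dose v 4 low dose (protocol 2.8.1); three Time levels (SAP 6.4.1); randomisation after baseline (SAP 4.0); significance level 0.05 (protocol 2.8.3), taken here as two-sided. The documents give no effect size, SD, correlation or power, so there is no figure of the plan's to reproduce.

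**Assumptions.** Outcome SD 1 at every visit, equal correlation r between visits (0.3 / 0.5 / 0.7), normal scores, and a difference of d = 1.5 SD at both post-baseline visits. Let h = 1/8 + 1/4 = 0.375.

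**1. What the literal main effect estimates.** With true differences 0, d1 and d2 at the three visits, it estimates (0 + d1 + d2)/3. The mean post-baseline effect is (d1 + d2)/2. The ratio is 2/3, whatever d1 and d2 are.

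**2. Chance baseline gap.** Its SD is √0.375 = 0.612 outcome SD. P(|gap| > 0.5 SD) = 2 × [1 − Φ(0.5/0.612)] = 41.4%. Given a gap g, the literal main effect shifts on average by (1 + 2r)g/3, and unadjusted change by −(1 − r)g. For g = 0.612:

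| r | literal main effect | unadjusted change |
|---|---|---|
| 0.3 | +0.33 SD | −0.43 SD |
| 0.5 | +0.41 SD | −0.31 SD |
| 0.7 | +0.49 SD | −0.18 SD |

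**3. Power, closed form.**
- Literal main effect: noncentral t, 10 df, noncentrality (2d/3)/√[h(1 + 2r)/3] = 2.24 / 2.00 / 1.83.
- Main effect over the two post-baseline visits only: 10 df, noncentrality d/√[h(1 + r)/2] = 3.04 / 2.83 / 2.66.
- Parametric interaction: F(2, 20), noncentrality (2/3)d²/[(1 − r)h] = 5.71 / 8.00 / 13.33.

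**4. F1_LD_F1, by simulation.** ANOVA-type interaction statistic on mid-ranks of all 36 values; 6,000 runs per setting. The permutation version uses all C(12,4) = 495 allocations, which assumes unrestricted 8:4 randomisation.

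| Test | r = 0.3 | r = 0.5 | r = 0.7 |
|---|---|---|---|
| Literal main effect | 52% | 44% | 38% |
| Post-baseline visits only | 78% | 72% | 67% |
| Parametric interaction | 50% | 65% | 87% |
| F1_LD_F1, asymptotic | 52% | 65% | 83% |
| F1_LD_F1, permutation | 44% | 57% | 76% |

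With no effect, asymptotic F1_LD_F1 rejects in 7.7 / 7.0 / 7.1% of runs, and a separate simulation of 3,000 runs per setting gave about 7 to 8%. Its power is therefore slightly flattered. The permutation version rejects in 4.7 / 4.7 / 4.8%. The literal main effect and the parametric ANOVA interaction both reject in about 5%.

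**5. Where the order changes.** The literal main effect and the parametric interaction have equal power at r = 0.35 / 0.33 / 0.31 for d = 1.0 / 1.5 / 2.0. If only half the effect is present after session 2, simulated power (d = 1.5) is 33 / 27 / 24% for the literal main effect and 39 / 51 / 75% for the parametric interaction. In that case the interaction leads even at r = 0.3.

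**The case against.** **The goal sentence names only the two post-baseline visits.** This is the strongest reply. Read that way, there is no dilution and, under the assumptions above, power exceeds that of the interaction at r = 0.3 and 0.5. But this reading conflicts with the Time line directly below it, and it is still not the protocol's test. A main analysis should not leave that choice to the analyst.

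**The ANOVA prints the interaction anyway.** True, but 6.4.1 does not name it as the deciding test.

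**The two documents may not be a matched pair.** This stands as a limit. The protocol reviewed still lists the six-month visits that SAP 4.0 says Amendment 5 ended, so a later version may have rewritten 2.8.3. The SAP's front matter was not available to this review. What is certain is that these two texts differ and that the SAP text available does not explain why.

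Three stronger inferences are tempting, and the documents do not support them:
- *That the SAP test inflates false positives.* It does not: over repeated randomisations its type I error is 5%, and the conditional Bonferroni rule is stricter than the protocol's, not looser. Unadjusted change also carries a baseline gap, with the opposite sign.
- *That the interaction is always more powerful.* That depends on the correlation, which the documents do not give.
- *That the outcome data drove the change.* SAP 8.0 shows that data had been presented. Nothing shows that they informed 6.4.1.

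**Conclusion.** Wrong as written. The main efficacy test in SAP 6.4.1 differs from protocol 2.8.3 in effect, method and multiplicity rule, with no reason in the SAP text available. Followed literally, it does not test the change that SAP 3.1 and question 2 ask about.

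The two-thirds dilution follows from the listed levels and randomisation after baseline. The 0.61 SD baseline-gap figure needs only the 8:4 split and independent patients with a common SD; the 41% figure also assumes normality. The power comparison rests on assumed d, equal SDs and equal correlation, and does not decide the matter. The conclusion rests on the mismatch between the named test and the question, and on the unexplained departure.

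Confidence is high that the texts differ and that the literal test misses change. It is only moderate that the departure is unexplained, given the version gap.

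**What to change.** Name one primary test in 6.4.1, for example:

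> *Primary test: CAPS Global Score, condition-by-time interaction over Baseline, three weeks after session 2 and three weeks after session 3, by F1_LD_F1 (protocol 2.8.3), two-sided 0.05, unadjusted. Subscales and diagnostic criteria met are secondary, and any Bonferroni correction applies among them. The repeated-measures ANOVA is a sensitivity analysis, with its interaction as the effect of interest.*

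If an amendment changed 2.8.3, or the sponsor keeps another test, cite it and give the reason and its date relative to unblinding and the 2010–2011 presentations. Report the F1_LD_F1 interaction in any case.

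Beside the asymptotic p-value, report a permutation p-value that follows the actual randomisation scheme. Label it a supportive addition, since neither document plans it.

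For the PDS (SAP 6.4.2, Analysis #1), first reconcile the visits: SAP 3.2 lists no Stage 1 PDS three weeks after session 2, but Analysis #1 uses that time point. Then name the interaction there too.

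**Cost.** SAP wording and a re-run on data already held; subscale results become secondary. Under the assumptions above, compared with the post-visits-only reading, power falls at r = 0.3 (78% to 52% asymptotic, 44% by permutation) and at r = 0.5 (72% to 65% or 57%). It rises at r = 0.7 (67% to 83% or 76%).
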